### **8.2.2. Primary Analysis of the Primary Endpoints**

This study is designed to be exploratory and descriptive in nature and no formal hypothesis testing is planned. Therefore, descriptive statistics will be used to summarize the results for each Part/Period.

The observed number and percentage of patients with an absolute SALT score  $\leq 20$  versus those with an absolute SALT score  $> 20$ , will be reported by treatment group with 95% confidence intervals (using the binomial approximation with a Wald continuity correction). This analysis will be completed for the Efficacy Population. The results may also be displayed graphically. No p-values will be reported.

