5. INTRODUCTION

5.1. Overview of Alopecia Areata

Alopecia areata (AA) is an autoimmune disorder characterized by patches of non-scarring alopecia affecting scalp or scalp and body hair. Alopecia Areata is clinically heterogeneous, affects males and females, and has a prevalence rate of approximately 0.2% of the United States population (Safavi, 1992; Benigno, 2020). There is no preventative therapy or cure. Alopecia areata often presents as a cyclical disorder marked by unpredictable periods of hair loss and spontaneous regrowth, and variation in the degree or pattern of hair loss gives rise to different subtypes of alopecia areata, such as patchy, ophiasis, totalis, or universalis. Approximately 7% of patients have severe disease with almost complete hair loss and little or no regrowth (Villasante Fricke, 2015). Approximately 80% of alopecia areata patients experience the first episode of hair loss by 40 years of age and 40% by 20 years of age (Villasante Fricke, 2015). Alopecia areata can have a psychological impact with high rates of depression (Sellami, 2014) and anxiety reported, particularly in children and adolescents (Bilgic, 2013), and therefore, psychological counseling is often recommended as part of the standard of care (Al-Mutairi, 2011).

A cause for alopecia areata has not yet been identified, though as in other autoimmune disorders, genetic susceptibility and a wide array of environmental triggers are thought to be involved. Treatments for alopecia areata were previously limited to moderately effective intralesional corticosteroid injections or topicals, or aesthetic disguises such as makeup and wigs. Baricitinib (Olumiant®), a JAK kinase inhibitor, was recently approved by the US Food and Drug Administration (FDA) and the European Commission for treatment of adults with severe AA, demonstrating that this class of molecules can provide treatment options for patients.

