While there is some evidence in the literature to suggest that drug discontinuation following the regrowth of hair with JAK inhibitors leads to the loss of the regrown hair, there are no data describing the results of discontinuation of CTP-543 under these circumstances. Also, it is not known if the dose producing significant hair regrowth is required to maintain the hair regrowth or if a lower dose can support the maintenance of the established regrowth. Consequently, this study is designed to examine dose reduction and drug discontinuation following the regrowth of hair using 8 mg BID or 12 mg BID of CTP-543. In addition, this study will assess whether retreatment with CTP-543 can reestablish the level of hair regrowth originally found for individuals that do not maintain hair regrowth following dose modification.

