8.3. Method of Treatment Assignment and Blinding

Part A

Period 1: Patients will be randomized such that approximately N = 130 for 12 mg BID and N = 170 for 8 mg BID) in an attempt to have approximately equal numbers of patients eligible for Part A, Period 2. Randomization will be stratified by scalp hair loss into one of the following two categories: 1) Partial scalp hair loss (SALT ≥ 50 and < 95); 2) Complete or near-complete scalp hair loss (SALT ≥ 95).

The randomization schedule will be generated prior to study start. Tablets and packaging of 8 mg and 12 mg CTP-543 will be identical in appearance.

Period 2: For each dose group, patients identified as Responders in Period 1 will be randomized in a 1:1 ratio to a dose reduction arm or a placebo (drug discontinuation) arm. For the dose reduction arm, patients previously on 12 mg BID in Period 1 will be assigned to 8 mg BID and

patients previously on 8 mg BID will be assigned to 4 mg BID. Given the previous experience with the primary endpoint for Period 1, it is expected that approximately 50 patients from each dose group in Period 1 will be Responders. Consequently, it is expected that approximately 25 patients from each dose group will be assigned to dose reduction and 25 patients will be assigned to drug discontinuation in Period 2.

The randomization schedule will be generated at the end of Period 1. Patients previously on 12 mg BID in Part A, Period 1, will receive 8 mg or placebo tablets twice daily for up to 24 weeks. Patients previously on 8 mg BID in Part A, Period 1, will receive 4 mg or placebo tablets twice daily for up to 24 weeks. Tablets and packaging for 4 mg CTP-543, 8 mg CTP-543 and placebo will be identical in appearance.

Part B

For each dose group, patients identified as having a LOM following either *dose reduction* or *drug discontinuation* in Part A, Period 2 will be assigned back to the original dose they received in Part A, Period 1. Study drug dosing regimen will be blinded by administering 2 x 8 mg tablets or 2 x 12 mg tablets twice-daily for 24 weeks. Tablets and packaging of 8 mg and 12 mg CTP-543 will be identical in appearance.

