8.4. Rationale for Study Design, Doses, and Primary Endpoint

Double-blind, randomized, placebo-controlled studies are considered optimal for obtaining unbiased estimates of the efficacy and safety of investigational products. The Severity of Alopecia Tool (SALT) (Olsen, 2004) was introduced as part of investigative guidelines published by the National Alopecia Areata Foundation is widely used to assess the extent of the scalp surface hair loss in AA. The SALT has been used as the hair loss measurement scale in all the studies of CTP-543 in patients with alopecia areata to date. The 24-week duration of the Treatment Period has been shown to be sufficient in establishing hair regrowth with CTP-543 and to significantly differentiate active doses from placebo as well as differentiate between doses of CTP-543.

The selection of the 8 mg and 12 mg BID doses of CTP-543 for this study is supported by the efficacy and safety of CTP-543 observed in the completed and analyzed Phase 2 CP543.2001, CP543.2002, and CP543.2003 studies. Analysis of the primary efficacy endpoint in CP543.2001 showed that the proportions of responders (patients achieving at least a 50% relative reduction in SALT score from Baseline at Week 24) were significantly greater in the 8 mg BID group and 12 mg BID group compared with the placebo group (P < 0.001 for both) and compared with the 4 mg BID group (P = 0.030 and P = 0.003, respectively). For the analysis performed on the efficacy population, 9.3% of patients in the placebo group and 21.4% of patients in the 4 mg BID group were responders, compared with 47.4% in the 8 mg BID group and 58.3% in the 12 mg BID group. Results also showed a significantly greater proportion of responders in the 8 mg BID and 12 mg BID groups which had at least 50%, 75%, and 90% relative reduction in SALT score by Week 24 compared with both the placebo group and the 4 mg BID group.

Additionally, both the 8 mg BID group and the 12 mg BID group had significantly greater proportions of patients who achieved an absolute SALT score ≤20 at Week 24 compared with the placebo group. Achieving a SALT score ≤ 20 has been reported by AA patients and clinicians to represent clinically-meaningful treatment success for AA (Wyrwich, 2020). In the Wyrwich study, qualitative interviews were conducted in the US with hair expert dermatologists and AA patients who had experienced ≥50% scalp hair loss. The clinicians judged that 80%

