## **8.2. Primary Endpoints**

### Part A:

This study is designed to be exploratory and descriptive in nature and no formal hypothesis testing is planned. Therefore, descriptive statistics will be used to summarize the results regarding dose modification following successful hair regrowth for each dose group. In Part A, Period 1, a Responder is defined as having an absolute SALT score  $\leq 20$  at Week 24 of the Treatment Period. Only Responders will enter into Part A, Period 2 (Dose Modification) for the primary efficacy analysis. For Part A of the study, there are two co-primary efficacy endpoints. The first co-primary efficacy endpoint is the percentage of patients achieving LOM criteria (SALT  $> 20$ ) compared to the percentage of patients maintaining treatment success (SALT  $\leq 20$ ) for each of the following dose reduction conditions (Period 2 ONLY):

- 12 mg BID reduced to 8 mg BID
- 8 mg BID reduced to 4 mg BID

The second co-primary efficacy analysis is the percentage of patients achieving LOM criteria compared to the percentage of patients maintaining treatment success for each of the following drug discontinuation conditions (Period 2 ONLY):

- 12 mg BID to Placebo
- 8 mg BID to Placebo

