## **8.4. Secondary Endpoints**

Analyses for secondary endpoints will be performed using the Efficacy Population.

Missing values will not be imputed.

Concert Pharmaceuticals, Inc.  
Statistical Analysis Plan – CP543.2004

For the secondary endpoints of proportions or percentages of patients achieving specified improvement criteria (hereinafter, “secondary responder endpoints”), pairwise treatment group differences in percentages and 95% CIs will be calculated in Part A Period 1 only.

Observed counts and percentages of responders will be summarized by treatment group for each Part/Period. 95% confidence intervals for percentages of responders and/or non-responders will be calculated using the binomial approximation with a Wald continuity correction.

For the secondary endpoints of absolute or relative changes (hereinafter, “continuous secondary endpoints”), continuous secondary endpoints will be summarized with descriptive statistics only and no treatment differences will be calculated. Descriptive statistics will include the number of subjects with data, mean, standard deviation, median, minimum, and maximum.

For Part A Period 1 only, treatment differences for continuous secondary endpoints will be assessed with a mixed-effect model of repeated measures (MMRM). Baseline SALT score will be included as a model covariate. Treatment group comparisons at each visit will be based on least squares (LS) mean estimates. An unstructured covariance matrix will be used to model the within-subject errors. Should the model fail to converge, an alternative autoregressive covariance matrix will be used instead. The Kenward-Roger approximation will be used to estimate the denominator degrees of freedom. Assuming that the data are MAR, the estimates of the treatment differences calculated from the MMRM described above are unbiased. Standard descriptive statistics will be reported for each time point on the values and changes from baseline along with the LS means, standard errors, 95% CIs and differences between treatment groups reported with LS means, standard errors, and 95% CIs. P-values will not be displayed.

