## 8.5. Other Endpoints

### 8.5.1. Time to First LOM (Part A only)

Time to first LOM (in weeks) will be summarized descriptively with Kaplan-Meier methodology for patients in the Efficacy Population who entered Part A Period 2. Treatment sequence across Period 1 and Period 2 (8 mg BID to 4 mg BID, 8 mg BID to placebo, 12 mg BID to 8 mg BID, and 12 mg BID to placebo) will be used as strata to present quantiles (25%, median, 75%), if estimable. Ninety-five percent confidence intervals for the median will be presented, if estimable, using the Brookmeyer and Crowley (1982) method. If KM statistics are not estimable, standard descriptive statistics for non-censored patients will be displayed.

First LOM is defined as the first date where a patient has an absolute SALT score  $>20$  in Part A Period 2. Time in weeks will be calculated from the date of randomization in Part A Period 2, as

- (date of first LOM (or censored date) - date of Part A Period 2 randomization + 1)/7

Patients who do not experience LOM before completion of Part A Period 2 or otherwise prematurely discontinue from Part A Period 2 will be censored at their last study visit date where SALT was measured in Part A Period 2 of the study, or a maximum of 24 weeks.

A Kaplan-Meier plot over time will also be presented.

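### Responders are re-randomized 1:1 to a lower dose or placebo in Period 2, but no analysis estimates that difference; the per-arm interval is also unreliable near 0% or 100%.

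*SAP*

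**What the plan says.** **Design.** Protocol 8.3 states that for each dose group "Responders in Period 1 will be randomized in a 1:1 ratio to a dose reduction arm or a placebo (drug discontinuation) arm". About 25 patients are expected in each of the four Period 2 arms (Protocol 13.1). The design rationale in Protocol 8.4 opens with "Double-blind, randomized, placebo-controlled studies are considered optimal for obtaining unbiased estimates of the efficacy and safety of investigational products". Protocol 5.2.1 lists among the open questions "if a lower dose can support the maintenance of the established regrowth".

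**Primary analysis.** SAP 8.2 words each co-primary endpoint as the "percentage of patients achieving LOM criteria compared to the percentage of patients maintaining treatment success", condition by condition. SAP 8.2.2 says the two percentages "will be reported by treatment group with 95% confidence intervals (using the binomial approximation with a Wald continuity correction"). SAP 8.2.3 and 8.2.4 specify no sensitivity or secondary analysis of the primary endpoint.

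**Differences.** For secondary responder endpoints, SAP 8.4 says "pairwise treatment group differences in percentages and 95% CIs will be calculated in Part A Period 1 only". Model-based treatment differences for continuous endpoints are likewise confined to Period 1, and p-values are withheld. For time to first LOM, SAP 8.5.1 says the four treatment sequences "will be used as strata to present quantiles (25%, median, 75%), if estimable", with a confidence interval for each median. No hazard ratio or other contrast is planned. No Period 2 efficacy table title in SAP 15.4 names a between-arm difference.

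**The concern.** The second randomization creates two concurrent, comparable groups within each original dose, and no planned output uses that to produce an estimate. The comparison that SAP 8.2 does name is between LOM and maintained percentages in the same arm. Since one is 100% minus the other, it says nothing about one arm against another.

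This matters because Protocol 5.1 calls the disease a "cyclical disorder marked by unpredictable periods of hair loss and spontaneous regrowth". A maintained percentage on the lower dose cannot by itself show what that dose adds over stopping, because some patients may keep their hair, or lose it, whatever they take. The concurrent placebo arm can show it. Table 14.2.1.1, which holds the co-primary results, goes into the abbreviated report for the NDA submission. Readers will make the comparison anyway, with only single-arm intervals to hand.

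The second worry is the interval itself. In a Wald interval the variance term vanishes when an arm has no events or only events, so the interval is narrowest where a small sample says least.

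**Working it through.** **Inputs.** About 50 responders per dose group, split 1:1, gives 50/2 = 25 per arm, which reproduces the figure in Protocol 13.1. The confidence level is 95%, with the interval method as in SAP 8.2.2. The documents give no expected LOM rates, so all counts below are assumed or cover every possible outcome.

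**Planned per-arm interval** (no truncation at 0 or 100%; the SAP does not say): p ± [1.96·√(p(1−p)/n) + 1/(2n)], where 1/(2n) = 1/50 = 2 points.

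**Example: LOM in 18/25 on placebo and 10/25 on the lower dose.**
- 18/25: 0.72 ± (1.96·√(0.72·0.28/25) + 0.02) = 0.72 ± 0.196, or 52.4 to 91.6%.
- 10/25: 0.40 ± (1.96·√(0.40·0.60/25) + 0.02) = 0.40 ± 0.212, or 18.8 to 61.2%.
- These overlap between 52.4 and 61.2%.

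The Newcombe interval combines the Wilson limits of the two arms, here 52.4 to 85.7% and 23.4 to 59.3%:
- Difference = 0.72 − 0.40 = 0.32.
- Lower limit = 0.32 − √[(0.72 − 0.524)² + (0.593 − 0.40)²] = 0.045.
- Upper limit = 0.32 + √[(0.857 − 0.72)² + (0.40 − 0.234)²] = 0.535.

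The difference is 32 points (4.5 to 53.5), which excludes zero although the arm intervals overlap.

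**All outcomes at 25 per arm.** There are 325 pairs of counts with one arm above the other. The table counts those whose Newcombe interval excludes zero.

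| Pairs considered | Newcombe excludes 0 | Planned arm intervals overlap |
|---|---|---|
| All | 202 | 50 (25%) |
| Both arms 5/25 to 20/25 | 45 | 24 (53%) |

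These are shares of possible outcomes, each weighted equally. They are not probabilities. When both arms lie between 20 and 80%, the Newcombe interval is 43 to 52 points wide.

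**Coverage of the per-arm interval at n = 25** (exact binomial enumeration; true rates in steps of 0.1 point).

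| True rate | Planned | Wilson | Clopper-Pearson |
|---|---|---|---|
| 20–80%, mean (minimum) | 95.1% (90.8%) | 95.1% (92.3%) | 97.0% (95.1%) |
| 3–10%, mean | 78.5% | 95.8% | 98.7% |
| 8% or 92% | 87% | 95.5% | 98.8% |
| 5% or 95% | 72% | 96.6% | 99.3% |
| 3% or 97% | 53% | 96.2% | 99.4% |

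**At the ends.** For 0/25 the planned interval is −2.0 to 2.0%, against an exact upper limit of 13.7%. For 25/25 it is 98.0 to 102.0%, against an exact lower limit of 86.3%. Untruncated limits fall outside 0 to 100% for counts of 0 to 4 and 21 to 25.

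**The case against.** The strongest defence is that the scope is deliberate. Both documents call the study exploratory and descriptive, reduction and discontinuation are separate co-primary analyses, and no objective names lower dose against placebo. That explains the lack of tests and p-values. It does not explain the lack of an estimate, because the same SAP gives Period 1 differences with confidence intervals and no p-values.

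Other points stand in part:
- The question in Protocol 5.2.1 also invites comparison with continuing the original dose, and the design has no such arm. Lower dose minus placebo answers the narrower question of lower dose against stopping. It is still the contrast that the randomization supports.
- The four arms appear side by side with counts, so anyone can subtract and compute an interval. What is missing is a pre-specified estimate. Under SAP 8.1.3 a later one would have to be labelled post hoc.
- Overlap is not a fault of the planned interval. With Clopper-Pearson it is more common (68 of 202 pairs, 30 of 45 mid-range) and with Wilson about the same (52 and 24). The overlap figures support adding the difference, not changing the per-arm method.
- The end-of-range weakness depends on rates that the documents do not give. Limits beyond 0 or 100% could simply be truncated, but truncation leaves 0 to 2.0% and 98.0 to 100% unchanged as misleading intervals.
- A difference placed in Table 14.2.1.1 inherits that table's rules: the Efficacy Population, analysis as treated, and the last observed SALT, under which a patient who leaves before LOM counts as maintained.

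**Conclusion.** The concern holds. No between-arm estimate is planned for the randomized Period 2 comparison, and the descriptive label does not account for that. At about 25 per arm, single-arm intervals are a poor substitute: they overlap in a quarter of all outcomes where the difference interval excludes zero, and in about half when both arms are mid-range.

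The interval point is secondary and conditional. The planned method matches Wilson on average between 20 and 80%, and fails below about 8% or above about 92%. For the primary table this is a risk, not a certainty. It is more likely to bite in the early by-visit LOM and restoration tables, which use the same method. Part B arms contain only patients with LOM, so they will usually be smaller than 25.

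The change should be made, but the trial does not turn on it: no test, decision rule or sample size depends on this. The numbers assume 25 per arm and an untruncated planned interval.

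**What to change.** 1. In Table 14.2.1.1, add for each original dose group the LOM difference, placebo minus dose reduction, with a Newcombe 95% CI. Label it descriptive and give no p-value, as SAP 8.4 already does for Period 1. Footnote the population and the last-observed-SALT rule that it inherits.
2. In SAP 8.2.2 and 8.4, replace the Wald continuity-corrected interval with Clopper-Pearson or Wilson.
3. Reword SAP 8.2 so that each co-primary endpoint is the percentage with LOM in each arm. Record the changes in SAP 13, since the protocol carries the same co-primary wording.

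**Cost.** Two table rows, one software option, and text edits; no new data or visits. Intervals near 0% or 100% become wider. Mid-range they become slightly narrower: for 12/25 the width is 43.2 points as planned, 40.9 with Clopper-Pearson and 36.5 with Wilson. Wilson coverage can dip to 92.3% mid-range; Clopper-Pearson stays at or above 95%. The difference intervals will be wide, and the report should say so.

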### **8.2.3. Sensitivity Analyses of the Primary Analysis**

No sensitivity analyses specified.

### **8.2.4. Secondary Analyses of the Primary Endpoint**

No secondary analyses specified.

## **8.3. Key Secondary Endpoints**

No key secondary endpoints specified.

## **8.4. Secondary Endpoints**

Analyses for secondary endpoints will be performed using the Efficacy Population.

Missing values will not be imputed.

Concert Pharmaceuticals, Inc.  
Statistical Analysis Plan – CP543.2004

For the secondary endpoints of proportions or percentages of patients achieving specified improvement criteria (hereinafter, “secondary responder endpoints”), pairwise treatment group differences in percentages and 95% CIs will be calculated in Part A Period 1 only.

Observed counts and percentages of responders will be summarized by treatment group for each Part/Period. 95% confidence intervals for percentages of responders and/or non-responders will be calculated using the binomial approximation with a Wald continuity correction.

For the secondary endpoints of absolute or relative changes (hereinafter, “continuous secondary endpoints”), continuous secondary endpoints will be summarized with descriptive statistics only and no treatment differences will be calculated. Descriptive statistics will include the number of subjects with data, mean, standard deviation, median, minimum, and maximum.

For Part A Period 1 only, treatment differences for continuous secondary endpoints will be assessed with a mixed-effect model of repeated measures (MMRM). Baseline SALT score will be included as a model covariate. Treatment group comparisons at each visit will be based on least squares (LS) mean estimates. An unstructured covariance matrix will be used to model the within-subject errors. Should the model fail to converge, an alternative autoregressive covariance matrix will be used instead. The Kenward-Roger approximation will be used to estimate the denominator degrees of freedom. Assuming that the data are MAR, the estimates of the treatment differences calculated from the MMRM described above are unbiased. Standard descriptive statistics will be reported for each time point on the values and changes from baseline along with the LS means, standard errors, 95% CIs and differences between treatment groups reported with LS means, standard errors, and 95% CIs. P-values will not be displayed.

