13.1. Sample Size Rationale

Approximately 300 patients will be randomized for Part A, Period 1 of the study. Allocation to each of the dose groups will be slightly imbalanced (approximately N= 170 for 8 mg BID and N= 130 for 12 mg BID) to attempt to get approximately 50 Responders per dose group to enter the Period 2 dose modification Phase. It is anticipated that there will be approximately 25 patients in each dose reduction and drug discontinuation arm for each dose group in Period 2. A sample size of 25 patients per arm should be adequate for describing the effects of dose modification in patients previously experiencing hair regrowth.

There is no formal hypothesis testing and consequently sample size was not based on power calculations.

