## 6.2. Demographic and Other Baseline Characteristics

Demographic characteristics (i.e., sex, ethnic origin, race, age, and calculated body mass index) will be collected at the Screening Visit, between Day -28 and -1, and detailed on the eCRF.

Demographic characteristics will be summarized using descriptive statistics for all randomized patients by treatment group and overall, for each of Part A Period 1, Part A Period 2, and Part B.

Concert Pharmaceuticals, Inc.  
Statistical Analysis Plan – CP543.2004

Baseline characteristics will be summarized using descriptive statistics for all randomized patients by treatment group and overall, for each study part, and will include the following:

- Baseline total SALT score
  - Note: Baseline total SALT score for Part A Period 2 will be the last SALT score obtained prior to dosing in Part A, Period 2 (ie, Week 24 SALT assessment from Part A, Period 1). Part B baseline total SALT score will be the last SALT score obtained in Part A, Period 2 prior to re-randomization into Part B.
- Alopecia areata classification (randomization strata): partial scalp hair loss (SALT  $\geq$  50 and < 95); complete or near-complete scalp hair loss (SALT  $\geq$  95)
- duration of current episode in years (calculated as: [date of randomization – date of current episode onset + 1] / 365.25)
- nasal hair involvement

For Part A Period 1, whether the patient has experienced any past and/or concomitant diseases, conditions, or exposures to serious infections (such as HIV), or past surgeries will also be summarized with baseline characteristics.

Other co-morbidities may be identified and included as baseline characteristics.

All demographics and baseline characteristics will also be listed within a by-patient data listing for all randomized patients.

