### 7.2. Randomization

#### Part A Period 1

Patients will be randomized such that approximately N = 130 for 12 mg BID and N = 170 for 8 mg BID in an attempt to have approximately equal numbers of patients eligible for Part A, Period 2. Randomization will be stratified by scalp hair loss into one of the following two categories: 1) Partial scalp hair loss (SALT  $\geq$  50 and  $<$  95); 2) Complete or near-complete scalp hair loss (SALT  $\geq$  95).

The randomization schedule will be generated prior to study start. Tablets and packaging of 8 mg and 12 mg CTP-543 will be identical in appearance.

#### Part A Period 2

For each dose group, patients identified as Responders in Period 1 will be randomized in a 1:1 ratio to a dose reduction arm or a placebo (drug discontinuation) arm. For the dose reduction arm, patients previously on 12 mg BID in Period 1 will be assigned to 8 mg BID and patients previously on 8 mg BID will be assigned to 4 mg BID. Given the previous experience with the primary endpoint for Period 1, it is expected that approximately 50 patients from each dose group in Period 1 will be Responders. Consequently, it is expected that approximately 25 patients from each dose group will be assigned to dose reduction and 25 patients will be assigned to drug discontinuation in Period 2.

The randomization schedule will be generated at the end of Period 1. Tablets and packaging for 4 mg CTP-543, 8 mg CTP-543 and placebo will be identical in appearance.

Part B

For each dose group, patients identified as having a LOM following either *dose reduction* or *drug discontinuation* in Part A, Period 2 will be assigned back to the original dose they received in Part A, Period 1. Study drug dosing regimen will be blinded by administering 2 x 8 mg tablets or 2 x 12 mg tablets twice-daily for 24 weeks. Tablets and packaging of 8 mg and 12 mg CTP-543 will be identical in appearance.

A by-patient listing of randomized treatment group and randomization number will be presented for each Part/Period.

All study patients, Investigators, and site study staff will be blinded to study drug assignment for the duration of the study.

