## 8.6. Examination of Subgroups

No subgroup analyses are planned.

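### The Period 1 responder differences name no interval method and do not use the SALT stratum of the randomisation, so a little precision may be given away

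*SAP*

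**What the plan says.** SAP 7.2 describes the Period 1 randomisation: "Randomization will be stratified by scalp hair loss into one of the following two categories", namely SALT ≥50 and <95, and SALT ≥95. Protocol 8.1 and 8.3 say the same.

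For the secondary responder endpoints, SAP 8.4 plans that "pairwise treatment group differences in percentages and 95% CIs will be calculated in Part A Period 1 only". These endpoints are SALT ≤20 at six visits (SAP 8.4.1) and SPRO, CGI-I and PGI-I at four visits each (SAP 8.4.2, 8.4.3 and 8.4.5). The section gives an interval method for the percentage within a treatment group, which "will be calculated using the binomial approximation with a Wald continuity correction". It gives none for the difference between groups.

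For the continuous Period 1 endpoints the same section specifies an MMRM and states: "Baseline SALT score will be included as a model covariate". The responder differences have no counterpart to this.

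Outside the description of the randomisation, the stratum appears in the SAP only as a baseline characteristic to be tabulated (SAP 6.2: "Alopecia areata classification (randomization strata): partial scalp hair loss"). SAP 8.6 says: "No subgroup analyses are planned". The list of changes in SAP 13 is silent on the matter.

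**The concern.** Stratified randomisation balances the arms on the stratum, so differences between strata no longer contribute to the chance variation of the dose comparison. A variance computed as if there had been no strata still counts that component. When the stratum predicts response, the resulting interval is too wide and covers more often than 95%.

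For SALT ≤20 a stratum effect is likely from the definitions alone. A patient starting at SALT ≥95 must fall by at least 95 − 20 = 75 points. A patient in the partial-loss stratum needs less than 75, and as little as 50 − 20 = 30. The sponsor already treats baseline SALT as worth adjusting for in the MMRM.

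At stake is the precision of 6 + 3 × 4 = 18 Period 1 intervals for 12 mg against 8 mg. The four tables that hold the responder endpoints are all marked for the abbreviated report in SAP 15.4. Missing values are not imputed, so the patients analysed at a visit may also be less well balanced on the stratum than those randomised. A stratum-weighted difference would correct for that; the documents give nothing from which to size it.

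**Working it through.** **Inputs from the documents.** Protocol 13.1 gives "approximately N= 170 for 8 mg BID and N= 130 for 12 mg BID", chosen "to attempt to get approximately 50 Responders per dose group to enter the Period 2 dose modification Phase". It states no response rate, interval width or power, so there is no precision figure to reproduce. The implied Week 24 rates are 50/170 = 29.4% and 50/130 = 38.5%, a difference of 9.0 points. They are back-calculated and so fit the allocation by construction.

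**Assumptions.** The documents give no stratum shares and no response rates by stratum. I take a partial-loss share f of 50% (range 30–70%) and a gap g in response rate between the strata of 0 to 40 points. The gap is the same in both arms, allocation is balanced within strata, and no data are missing.

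**Unstratified interval** (unpooled Wald, without continuity correction):

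variance = p8(1−p8)/170 + p12(1−p12)/130 = 0.20761/170 + 0.23669/130 = 0.003042; half-width = 1.96 × √0.003042 = 10.81 points.

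**Stratified interval.** Weight the stratum differences by stratum share, which equals the Mantel-Haenszel weighting when allocation is balanced within strata. Each p(1−p) is then replaced by its average within strata, p(1−p) − f(1−f)g². For f = 0.5 and g = 0.20 the deduction is 0.25 × 0.04 = 0.01:

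variance = 0.19761/170 + 0.22669/130 = 0.002906; half-width = 1.96 × √0.002906 = 10.57 points, so the unstratified interval is 10.81/10.57 − 1 = 2.3% wider.

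| Gap between strata (points) | Stratified half-width, f = 50% | Unstratified wider by | Excess half-width (points) | Wider by, f from 30% to 70% |
|---|---|---|---|---|
| 0 | 10.81 | 0% | 0 | 0% |
| 10 | 10.75 | 0.6% | 0.06 | 0.5–0.6% |
| 20 | 10.57 | 2.3% | 0.24 | 1.9–2.3% |
| 30 | 10.25 | 5.4% | 0.56 | 4.5–5.4% |
| 40 | 9.80 | 10.3% | 1.01 | 8.5–10.3% |

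**Coverage.** I simulated 100,000 trials per scenario, with stratum sizes fixed in each arm and f = 50%. The unstratified Wald interval covered 94.9%, 95.3%, 95.9% and 96.9% of the time at gaps of 0, 20, 30 and 40 points. The stratified interval stayed at 94.7–94.8%.

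**The unnamed method matters about as much.** If the continuity correction for single percentages were carried over to the difference, it would add 0.5 × (1/170 + 1/130) = 0.68 points to the half-width. That is slightly more than the stratum effect at a 30-point gap.

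**Early weeks.** If the partial-loss stratum responds better, g cannot exceed p/f. The deduction f(1−f)g² is then at most p²(1−f)/f, which is p² at f = 50%. Compared with p(1−p), that is a share p/(1−p), which is small when few patients have responded.

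**The case against.** Most of the case against the point concerns its size and certainty, and much of it stands.

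- **The method is unstated.** A reader might infer that the SAP prescribes a crude, unstratified interval. It does not say so: it prescribes no method for the difference. That the stratum is left out is read from silence. This stands, and it is a further reason to write the method down.
- **The size is assumed.** A reader might take it as fact that the intervals will be materially too wide. That depends on stratum shares and rates that the documents do not give. At a 10-point gap the effect is negligible, and at 40 points it is about one point on a half-width of 10.8.
- **Nothing is decided on these intervals.** The study is descriptive, with no tests, p-values or power basis. The effect on width is conservative, and an unadjusted difference is a legitimate descriptive summary.
- **The SALT argument does not carry over.** CGI-I and PGI-I rate change against the patient's own starting point, and SPRO rates current satisfaction. The documents give no stratum effect for any of the three.
- **This is not the only dose comparison of response.** SAP 8.2 also says that the Part B treatment sequences, which include both doses, are to be compared on restoration of regrowth, although no interval for a difference is planned there.
- **Partial cover exists.** The MMRM adjusts the continuous endpoints for baseline SALT, and the strata are tabulated by arm, so a marked imbalance would be seen.

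None of this supplies a method or an adjustment for the responder differences themselves.

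**Conclusion.** The point holds as a minor, free improvement. SAP 8.4 plans Period 1 responder differences with 95% CIs but names no interval method for them and makes no use of the randomisation stratum. If the stratum predicts response, an unstratified interval is conservative. For Week 24 SALT ≤20 it would be about 0.6% to 10% wider than the stratified one over gaps of 10 to 40 points, given the back-calculated response rates, 50:50 strata and equal gaps in both arms. Shares between 30% and 70% give similar figures. With no stratum effect there is no loss.

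A reader might go further and infer bias, under-coverage or a threat to the trial's main results. The documents do not support that. The consequence is lost precision on secondary descriptive endpoints, and the Period 2 co-primary and Part B primary analyses are unaffected.

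**What to change.** Add one sentence to SAP 8.4: Period 1 responder differences are Mantel-Haenszel stratum-weighted risk differences by the randomisation category (SALT ≥50 and <95; SALT ≥95), with a named stratified 95% CI, for example stratified Newcombe. Keep the crude percentages by arm alongside, so that readers still see the observed rates.

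This names the missing method and aligns the responder analysis with the randomisation. It needs no new data, patients or visits, because the stratum is already recorded. The cost is the sentence, a standard software option, and a footnote to Tables 14.2.2.1, 14.2.3.1, 14.2.3.2 and 14.2.3.3.
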